A study published in 2016 implemented an intervention using a bilingual and interactive educational program on tablets regarding breastfeeding; this achieved increased knowledge of the subject and breastfeeding intention (1). In 2017, another study developed an intervention program through a website that consisted of exchanging advice, resolving doubts, and providing follow-up to participating breastfeeding mothers. The study concluded that the program had a positive effect on breastfeeding duration rates during the 6-month follow-up period (2). In 2018, a study conducted in Thailand consisted of an intervention to promote breastfeeding through a mobile application. It was concluded that the application has high utility for mothers, but usability was low due to design aspects (3).

In 2020, an observational study based on the description of a breastfeeding mobile application found that the support provided by the tool is linked to the needs corresponding to the infant's developmental stage. Between 15 days and 3 months of age, mothers consult on topics such as breastfeeding crises/complications and returning to work. From 3 months to 1 year, mothers seek support on issues related to complementary feeding and weaning. When the user's infant reaches 1 year of age, the most searched topics are weaning and breastfeeding (4)

National Background

A study conducted in Lima, Peru, in 2019 regarding beliefs, attitudes, and practices (BAP) surrounding breast milk (BM) donation found that 98.2% of those surveyed believe that BM is the best food for both healthy and ill newborns. Additionally, while 75.7% had heard of Human Milk Banks (HMB), they were unaware of their locations. Furthermore, although the majority of participants agreed with donating to an HMB, only 16.5% had ever donated (5).

State of the Art

BM provides the ideal balance of nutrients for the infant, containing bioactive ingredients such as immunoglobulins, hormones, oligosaccharides, and others (6,7). Children who do not receive BM are at a higher risk of suffering from gastrointestinal, respiratory, and urinary infections, which may be more severe and lead to hospital admissions; in the long term, they face an increased risk of asthma, obesity, diabetes mellitus, and cancer (8).

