At a global level, evidence shows that during the 2009–2015 period, there were 1,563,240 female donors, with South America being the region with the highest percentage of donors (96.6%) (19). In Peru, the first HMB was founded in 2010 at the NMPH. The number of donors increased from 368 to 1,642 in the 2010–2018 period (10). However, this increase is insufficient to cover the growing annual rate of preterm births (1,620), which demand approximately 500 liters of donated BM per month (20). This situation has worsened in the context of the COVID-19 pandemic, which reduced the number of monthly donors from 200 to 50 (20).

Evidence shows that factors related to the low number of BM donors include perceptions, beliefs, and attitudes such as: the belief that donating carries a risk of transmitting HIV or cancer, and a low interest in donating due to lack of knowledge (21).

As part of the profile development for this project, interviews were conducted with breastfeeding mothers and healthcare personnel to understand their perception of BM donation. The results revealed a lack of knowledge regarding HMBs and BM donation, and a perception among mothers that they should exclusively donate when they have surplus milk. However, upon learning about the assistance they could provide to newborns, they adopted a positive attitude toward donation (22).

Based on the above, there is clear evidence of a real problem concerning the deficit of human milk donors in Peru.

IV. Justification:

Considering that the proportion of deaths among preterm newborns in the country has increased over the last decade (from 62.6% in 2011 to 71% in 2019) (23), it is necessary to promote knowledge regarding BM donation to favor an increase in the volume of such donations.

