- Breastfeeding mothers who have access to an Internet connection.
- Breastfeeding mothers who have the necessary equipment to access platforms with video-calling capabilities.
- Breastfeeding mothers who are proficient in the use of platforms with video-calling capabilities.

Exclusion Criteria:

- Mothers for whom breastfeeding is contraindicated.
- Breastfeeding mothers with a diagnosis of mental illness.
- Breastfeeding mothers who are or have been donors to the Human Milk Bank of the National Maternal and Perinatal Hospital.

Sampling for Intervention Development

Population: Breastfeeding mothers treated at the National Maternal and Perinatal Hospital (NMPH).

Sample Size: The sample size was determined using the OpenEpi program, with the option “Sample size to compare two means”, considering a IC of 95%, a power of 80%, a sample size ratio equal to 1, a minimum mean difference of 2.1 (in the breastfeeding knowledge score) and a SD of 3.4 for both groups, similar to that found in the study by Joshi et al (1).

Therefore, the net sample size required for this study was 86 participants, distributed as follows: 43 in the control group and 43 in the intervention group. However, considering a potential loss of 30% between the initial and the final assessment, the sample size was increased by 112 mothers in total.

Inclusion Criteria:

- Breastfeeding mothers within 40 days postpartum.
- Breastfeeding mothers with living children.
- Breastfeeding mothers with an active Internet connection.
- Breastfeeding mothers who possess the technological equipment required to access the innovative technological tool (smartphone, tablet, or computer).
- Breastfeeding mothers residing within the jurisdiction of the National Maternal and Perinatal Hospital.

Exclusion Criteria:

- Breastfeeding mothers who are illiterate.
- Breastfeeding mothers with a diagnosis of mental illness.
- Breastfeeding mothers with significant difficulties in operating technological equipment.
- Breastfeeding mothers who are current users of any milk bank.
- Breastfeeding mothers who are or have been donors to the Human Milk Bank of the National Maternal and Perinatal Hospital.

Techniques and procedures

The time of participation in the study will be approximately 3 months, divided into the following phases: enrollment (15 days), baseline assessment (7 days), exposure to the intervention (60 days), and final assessment (7 days).

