could donate their breast milk, nor were they aware of the existence of HMB. The mothers also expressed a favorable attitude towards human milk donation, but stated that they had not engaged in that practice due to a lack of knowledge.

Stage 2: Identification of Needs

An empathy map was drawn up with the responses obtained to identify the needs of the users and the prioritization of the issues to be addressed regarding breastfeeding and milk donation. In this second stage, the mothers' need for easily accessible information on human milk donation, the requirements to be a donor, the mechanisms for donating, and the locations of human milk banks were identified.

Stage 3: Ideation of Solutions

A team of 6 researchers devised different innovative solutions (eg, digital educational booklet, mobile app, telephone counselling, SMS, and MMS), which were then evaluated using the impact and innovation matrix; a vote was taken considering the criteria of impact, innovation, added value, and scalability. Finally, the mobile app was the top-rated vote.

Stage 4: Prototyping

The intervention is prototyped as a mobile app, based on the HCD model [27,31]. This model comprises sequential phases that range from defining the user requirement, designing the proposal, and through the implementation, verification, and maintenance of the intervention with the mobile app. The prototype was developed following the sequence previously described, which involved outlining the didactic content, the bibliographic search for educational content, the search for graphic resources, and the design of the screens, sections, and navigation routes.

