With the final version of the technological innovation tool, the randomized controlled trial will be implemented for a period of 60 days. The research team will continuously conduct field evaluations of the tool's performance (verification) and ensure the maintenance of the intervention through push notifications, reminders, text messages (SMS), or other complementary resources. At this stage, a baseline and final measurement of indicators will also be assessed for both the intervention and control groups using a KAP questionnaire developed by the researchers. As part of this last stage, the qualitative component of the evaluation of the effect of the mobile intervention will be implemented. Purposive sampling will be used to recruit participants. Any breastfeeding mother from the intervention group who has completed the mobile intervention will be eligible to take part.

Analysis Plan

Qualitative Analysis Plan

The information gathered from the in-depth interviews will be transcribed, processed, and analyzed using specialized qualitative data analysis software. Consequently, matrices and graphic organizers will be generated.

Statistical Analysis Plan

The information collected during the intervention will be processed in MS Excel and analyzed using IBM SPSS statistical software.

Inferential analysis will be by intention to treat (ITT), to ensure the equivalence of the study groups. The sociodemographic and baseline characteristics of the control and intervention groups will be compared using Pearson's Chi-square test, Fisher's exact test, or Student's t-test, depending on the type of variable.

To determine the effect of the intervention, changes in milk donation knowledge scores among breastfeeding mothers in the intervention group will be compared with the control group throughout the study period (baseline and endline variation) using a double difference regression model.

For qualitative variables (attitudes, practices), a Cochran's Q test will be applied to evaluate changes following the intervention period. Regarding donation practices, Fisher's exact test will be applied, and the Odds Ratio (OR) will be calculated to determine the utility of the intervention in breast milk donation. Finally, only descriptive statistics will be presented regarding user satisfaction.

Ethical Considerations

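### Attitude is handled as a categorical, by implication yes/no, outcome instead of a score, which costs power for Specific Hypothesis 2, and the named test does not compare the arms

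*Combined protocol and SAP*

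**What the plan says.** Section VI makes improved attitude toward donation the second specific hypothesis, and section VII repeats it as an objective. The Statistical Analysis Plan in section VIII compares changes in knowledge scores between arms with a double-difference regression. Attitude is treated differently: "For qualitative variables (attitudes, practices), a Cochran's Q test will be applied to evaluate changes following the intervention period". The same paragraph adds Fisher's exact test and an odds ratio, but for donation practices only.

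The KAP questionnaire was developed by the researchers. The document does not describe its attitude items, scoring or any cut-off. It gives no expected baseline, target change or power for attitude. The sample size rests on knowledge alone: "a minimum mean difference of 2.1 (in the breastfeeding knowledge score) and a SD of 3.4 for both groups".

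On where attitudes start, the document is mixed:
- Stage 1 (12 interviews): "The mothers also expressed a favorable attitude towards human milk donation".
- National Background (2019 Lima survey): "although the majority of participants agreed with donating to an HMB, only 16.5% had ever donated".
- Problem Statement (profile interviews): "upon learning about the assistance they could provide to newborns, they adopted a positive attitude toward donation".
- The Executive Summary and Problem Statement also blame attitudes, fear of disease transmission and low interest for the shortage of donors.

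**The concern.** There are two problems. First, Cochran's Q tests change across repeated measurements in the same people. With one baseline and one endline it is a McNemar-type test, so applied within an arm it shows whether mothers changed, not whether the app changed them more than the leaflets did.

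Second, the test implies that attitude is reduced to two categories. Replacing Cochran's Q with a valid between-arm test on the same variable would leave that loss of information in place. The trial is small and sized for a continuous outcome, so a null attitude result could not be told apart from an insensitive endpoint. If most mothers in both arms end up favourable, the loss is greater. The leaflet arm receives information on the same topic, which makes that possible.

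**Working it through.** **The plan's own figure.** The inputs, from the sample-size paragraph, are a difference of 2.1, SD 3.4, 95% confidence (two-sided assumed), 80% power and 1:1 allocation.

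- n per arm = 2 × [3.4 × (1.960 + 0.842) / 2.1]² = 41.1, so 42. The t-based solution is 42.13, so 43. The stated 86 net (43 per arm) is reproduced.
- 86 × 1.30 = 111.8, so the stated 112 is reproduced. If 30% are lost, 112 × 0.70 = 78.4 remain, about 39 per arm.

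**Assumptions for attitude.** The document gives no effect size for attitude, so I borrow 2.1 / 3.4 = 0.62 SD from knowledge. I take a normal underlying attitude and let the leaflet-arm endline favourable proportion p range from 50% to 95%.

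**Attitude as a score, 43 per arm.** SE = 3.4 × √(2/43) = 0.733, and 2.1 / 0.733 = 2.864. Power = Φ(2.864 − 1.960) = Φ(0.904) = 0.82.

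**Attitude as a split, compared between arms.**
- App-arm proportion: q = Φ(Φ⁻¹(p) + 0.618).
- Normal-approximation power: Φ[(q − p − 1.960 × SE₀) / SE₁], where SE₀ uses the pooled proportion and SE₁ the separate ones.
- Relative efficiency of split to score: φ(z)² / [p(1 − p)], with z = Φ⁻¹(p).

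Example at p = 0.50: q = 0.732; SE₀ = √(0.616 × 0.384 × 2/43) = 0.105; SE₁ = √[(0.250 + 0.196)/43] = 0.102. Power = Φ[(0.232 − 0.206) / 0.102] ≈ 0.60.

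| Leaflet arm | App arm | Fisher (exact power) | Normal approx. | Relative efficiency |
|---|---|---|---|---|
| 50% | 73% | 53% | 60% | 0.64 |
| 60% | 81% | 49% | 56% | 0.62 |
| 70% | 87% | 40% | 50% | 0.58 |
| 80% | 93% | 30% | 41% | 0.49 |
| 90% | 97% | 10% | 27% | 0.34 |
| 95% | 99% | 1% | 17% | 0.22 |

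At 39 per arm the score has 78% power. The split has 47% (Fisher) at p = 50% and 27% at p = 80%.

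**How much is ceiling?** At 50% there is no ceiling, yet power already falls from 82% to 53–60%. That part is the cost of dichotomising, plus Fisher's conservatism in the lower figure. The further fall down the table is the ceiling. As a separate check, suppose the app arm reached 100% favourable with 39 per arm. Power would be 85% (Fisher 82%) if the leaflet arm stood at 80%, 72% (54%) at 85%, and 53% (19%) at 90%. Headroom alone becomes prohibitive only from about 85% upward.

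**Do the documents fix p?** No. A majority means anything above 50%, and the survey was done at another hospital. Even if all 12 interviewees were favourable (an assumption), the exact lower 95% limit is 0.025^(1/12) = 0.74.

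**The case against.** A reader might infer that the endpoint already sits near its ceiling and that the attitude objective will show no effect whatever the app does. The documents do not support that. They report no favourable proportion, and the evidence is 12 qualitative interviews and an unquantified majority elsewhere. Other statements point to negative beliefs and low interest, which leave room to improve. The profile interviews show that attitude can move with information. They count against a between-arm difference only if leaflets move it equally well, which nothing in the document establishes. This part of the objection stands.

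Four further points have weight:
- The dichotomy is inferred from the test. No favourable/unfavourable endpoint is written down, and a strict cut-off could leave ample headroom.
- The 0.62 SD shift has no stated link to attitude.
- Fisher's test is planned for practices, not attitude, so the Fisher column is the pessimistic end.
- The 82% assumes an unbounded score. A summed Likert score has a maximum and could bunch there too.

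It is also fair to say that acting on approval is already covered by the third objective. Adding graded items on intention to donate would be a design preference, not the repair of an error.

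None of this removes the two core points. The named test does not compare the arms, and under these assumptions the split has less power than the score at every proportion examined.

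**Conclusion.** The concern holds as a loss of sensitivity and a missing between-arm analysis. Under the stated assumptions, the score's power of about 82% (a best case) falls to 53–60% with no ceiling, 30–41% at 80% favourable and 10–27% at 90%. The recommendation does not depend on where in the range of 50% to 95% the leaflet arm ends.

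A ceiling is a plausible aggravating factor that the plan does not address, and it should be described only as that. The sizes rest on the borrowed 0.62 SD, a normal underlying attitude, 43 analysed per arm and binary coding inferred from Cochran's Q.

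**What to change.** In the Statistical Analysis Plan, define the attitude outcome as the summed attitude score of the KAP questionnaire, with graded items where possible. State the scoring rule. Compare the arms at endline in a regression adjusted for the baseline attitude score, and report the between-arm difference with its confidence interval. Give the favourable proportion by arm descriptively, with its cut-off fixed in advance.

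If the items are already graded, the cost is a few lines of SAP text. If they are yes/no, the questionnaire itself must change. The 5-point scale in Stage 5 measured usability and is not a ready-made attitude scale. A mean score difference is also less immediate to read than a proportion. Because the summed score may bunch near its maximum, its baseline distribution should be reported.

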Simultaneously, this work seeks to contribute to and foster the development of future research related to the proposed topic, as it is unfortunately not yet widely disseminated, and similar projects to the one proposed are currently lacking.

Finally, the use of this project as a baseline for a multicenter study is suggested, involving all HMBs in Peru to provide more robust and significant evidence. This would allow for an adequate approach to the target population, leading to an increase in the number of BM donors with the goal of decreasing the neonatal mortality rate and, consequently, generating a positive impact on the country's public health.

VI. Hipótesis:

General Hypothesis:

- The intervention through an Innovative Technological Tool promotes breast milk donation among breastfeeding mothers.

Specific Hypotheses

- The intervention through an innovative technological tool increases the knowledge level regarding breast milk donation among breastfeeding mothers.
- The intervention through an innovative technological tool improves the attitude toward breast milk donation among breastfeeding mothers.
- The intervention through an innovative technological tool increases the proportion of breastfeeding mothers who initiate breast milk donation practices.

VII. Objectives:

General Objective:

To evaluate the effect of an intervention using an innovative technological tool on the promotion of breast milk donation among breastfeeding mothers.

Specific Objectives:

- To measure the effect of an intervention using an innovative technological tool on the level of knowledge regarding breast milk donation among breastfeeding mothers.
- To evaluate the effect of an intervention using an innovative technological tool on the attitude toward breast milk donation among breastfeeding mothers.
- To identify the effect of an intervention using an innovative technological tool on the proportion of breastfeeding mothers who initiated breast milk donation practices.

VIII. Methodology:

Research Design

A randomized controlled trial (RCT) will be conducted.

Population and Sample

Sampling for the Qualitative Component

- **Population:** Breastfeeding mothers treated at the National Maternal and Perinatal Hospital (NMPH).
- **Sample Size:** 10 breastfeeding mothers (in-depth interviews), determined by non-probability sampling.

Inclusion Criteria:

- Breastfeeding mothers within 40 days postpartum.
- Breastfeeding mothers with living children.

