The development of the mobile intervention was based on the Human-Centered Design (HCD) approach (27). *AmamantApp* app includes modules on breastfeeding basics, benefits of breastfeeding for mother and child, breast milk donation, benefits of donating breast milk, myths and beliefs about human milk donation, requirements to be a donor, and where to donate.

To reduce bias, participants will be randomly assigned to the intervention and control groups in a 1:1 ratio according to their order of inclusion in the study. A master randomization list will be generated using the Spanish version of the free OxMaR software (28).

The intervention group will receive education on human milk donation via a mobile app, and the control group will receive information on human milk donation through printed leaflets. The app will be installed and explained to the mothers with hospital discharge orders on their mobile phones. The intervention will continue while the mothers are at home. The research team will hold an interactive session to introduce the mobile app to the participants. This will begin with an initial explanation of the app's features, followed by a period in which participants will be able to explore and use the application in real time. Furthermore, participants will receive weekly training on how to use the app to reinforce their knowledge of its operation.

The intervention period will last 60 days, during which knowledge, attitudes, and practices (KAP) will be assessed using a KAP questionnaire. This instrument will be administered face-to-face at baseline (pretest) and online via Google Forms after the intervention (posttest).

Design and Evaluation of the Mobile App

The process of designing the intervention with the Amamantapp app was based on Human Centered Design (HCD) through the application of the Design Thinking technique [29, 30]. This technique consisted of 6 stages:

Stage 1: Recognition

Aimed at empathizing, researchers defined the user profile, as well as the sociodemographic characteristics of the breastfeeding mothers. In this stage, 12 in-depth interviews were used to collect information concerning their KAP related to breastfeeding/breastmilk donation and the use of technology. At this stage, it was found that mothers were not aware that they

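### Attitude is tested only with Cochran's Q, a within-woman test, so Specific Hypothesis 2 has no planned app-versus-leaflet comparison

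*Combined protocol and SAP*

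**What the plan says.** Section VIII, Statistical Analysis Plan, assigns a test to each outcome.

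- **Knowledge:** "changes in milk donation knowledge scores among breastfeeding mothers in the intervention group will be compared with the control group throughout the study period", by a double difference regression. This is an explicit between-arm analysis.
- **Attitude and practices:** "For qualitative variables (attitudes, practices), a Cochran's Q test will be applied to evaluate changes following the intervention period".
- **Donation practices, in addition:** "Regarding donation practices, Fisher's exact test will be applied, and the Odds Ratio (OR) will be calculated to determine the utility of the intervention".

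Section VI, Specific Hypotheses, states the claim for attitude: "The intervention through an innovative technological tool improves the attitude toward breast milk donation among breastfeeding mothers". The matching objective in Section VII also asks for the effect of the intervention on attitude.

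Section VIII, Techniques and procedures, adds two relevant facts. The control arm is active: "the control group will receive information on human milk donation through printed leaflets". There are two measurements: "This instrument will be administered face-to-face at baseline (pretest) and online via Google Forms after the intervention (posttest").

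**The concern.** A hypothesis about the effect of the app needs a contrast between the randomised arms. Cochran's Q compares related binary responses from the same women. It can show that mothers changed over 60 days, but not that the app changed them more than the leaflet did.

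That matters here because change is plausible in both arms. Both receive donation information, and the Problem Statement in Section III reports that interviewed mothers became positive about donating once they learned how it helps newborns. A pre-post test can then be significant with no app effect at all, and for attitude the randomisation would go unused. The trial could report improved attitudes as an effect of the app on evidence that does not separate the two arms.

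**Working it through.** **1. Is there another test for attitude?** Three candidates in the Statistical Analysis Plan can be ruled out. The intention-to-treat sentence settles who is analysed, not which contrast is tested. The chi-square, Fisher and t-tests named beside it are for sociodemographic and baseline characteristics. The double difference model is for knowledge scores. Only Cochran's Q remains.

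**2. What Q measures with two time points.** Let b be the number of women moving to a favourable attitude and c the number moving away. Then

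Q = (b − c)² / (b + c), on 1 degree of freedom, significant at 5% if Q > 3.84.

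This is the uncorrected McNemar statistic. In a generated data set of 43 women both formulas gave 3.857. Arm does not appear in it.

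**3. Number of women.** The plan has no sample size for attitude, so the figures for knowledge are used. The plan's own figure reproduces: with difference 2.1, SD 3.4, two-sided 5% and power 80%, n = 2 × (1.960 + 0.842)² × 3.4² / 2.1² = 41.2, or 42 per arm. The t-based version gives 42.13, rounded up to the stated 43. If 30% of the 112 enrolled are lost, 112 × 0.70 / 2 = 39.2 per arm remain. The range is therefore 39 to 43 per arm.

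**4. An example with identical arms.** Assume 20% move to favourable and 5% move away in each arm of 43. The expected counts are b = 8.6 and c = 2.15.

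- Per arm: Q = 6.45² / 10.75 = 3.87, just significant.
- Pooled: Q = 12.9² / 21.5 = 7.74, clearly significant.
- Difference between arms in net change: 0.

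**5. Range over assumed rates.** The documents give no attitude rates, so the movement rates below are assumptions, equal in both arms (no app effect). With p the chance that Q is significant in one arm, obtained by exact enumeration, the chance of significance in the app arm only is p(1 − p). Pooled Q is also enumerated, with twice the number of women. The between-arm column is a simulated Wald test on the difference in net change. Each cell gives n = 39 / n = 43.

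| Moving to / away | Q in one arm, p | App arm only, p(1 − p) | Pooled Q | Between-arm test |
|---|---|---|---|---|
| 10% / 10% | 4.5% / 4.4% | 4.3% / 4.2% | 5% / 5% | 5.5% / 5.4% |
| 15% / 10% | 8.2% / 8.7% | 7.5% / 7.9% | 15% / 16% | 5.4% / 5.3% |
| 10% / 5% | 11.5% / 12.1% | 10.2% / 10.7% | 19% / 21% | 5.3% / 5.3% |
| 20% / 5% | 46.0% / 50.2% | 24.8% / 25.0% | 80% / 84% | 5.2% / 5.1% |
| 30% / 5% | 80.1% / 84.5% | 15.9% / 13.1% | 99% / 99% | 5.5% / 5.2% |
| 40% / 5% | 95.6% / 97.2% | 4.2% / 2.7% | >99.9% / >99.9% | 5.4% / 5.4% |

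**6. A second set of assumptions.** A separate simulation took favourable attitude from 50% to 60%, 70% or 80% in both arms of 43, with a latent pre-post correlation of 0.5. Pooled Q rejected in 37%, 91% and 99.9% of trials. App arm only occurred in 15.7%, 23.7% and 5.5%. The between-arm test rejected in 5.4%, 5.3% and 5.3%.

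**The case against.** Four points can be made for the plan, or against pressing this too far.

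**Practices are covered.** A reader might infer from the Cochran's Q sentence that Specific Hypothesis 3 also lacks a randomised test. The documents do not support that. The next sentence adds Fisher's exact test and an odds ratio to judge the utility of the intervention. It does not name the arms, but app versus leaflet is its natural reading.

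**The practice analyses need not conflict.** One might argue that Q on practices is nearly degenerate because the trial excludes "Breastfeeding mothers who are or have been donors to the Human Milk Bank of the National Maternal and Perinatal Hospital", and that it could contradict Fisher's test. But the KAP items are not shown, so the two tests may concern different variables. Even on one variable they answer different questions. The exclusions also do not expressly cover past donors to other banks. Nor is it safe to say that four new donors make Q significant: the chi-square approximation gives Q = 4 and p = 0.046, but the exact two-sided p is 2 × 0.5⁴ = 0.125.

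**The per-arm reading is not in the plan.** The plan does not say whether Q will be run per arm or pooled, or that significance in one arm only will be read as an effect. It would be tempting to quote 25% as the false-positive rate. That is the ceiling of p(1 − p), reached at p = 0.5, and it belongs to a decision rule that the plan never states. Attitudes may also be favourable already, as the National Background and Stage 1 of the app design suggest, which could leave less room to move.

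**Knowledge has a sound contrast.** The sample size rests on the knowledge score, and knowledge has a between-arm model.

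These points limit the scope and the size of the concern. None supplies a between-arm test for attitude.

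**Conclusion.** The analysis of attitude is wrong as written. Its only named test has no arm term, so it cannot answer Specific Hypothesis 2 or its objective. This follows from the text and needs no assumption about rates. The gap is limited to attitude.

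The size does depend on assumptions. With no app effect, 39 to 43 completers per arm and equal movement in both arms (10% to 40% towards favourable, 5% to 10% away), significance in the app arm only occurs about 3% to 25% of the time. Pooled Q rejects from about 5%, when there is no net change, to nearly 100%. A between-arm test stays near 5% throughout.

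**What to change.** - **Attitude:** replace Cochran's Q as the effect test with a between-arm comparison of endline attitude adjusted for the baseline value. Use ANCOVA if the attitude section is scored, or ordinal or binary logistic regression if it is categorical. Report the arm effect with a 95% CI. State how attitude is scored, since Q presupposes a yes/no variable and the text gives no rule for forming one.
- **Practices:** base the effect conclusion on Fisher's exact test and the odds ratio, and state that the comparison is app versus leaflet.
- **Within-arm change:** report any pre-post result (Q or McNemar) as descriptive only.

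The cost is SAP wording. Arm, pretest and posttest are already to be collected, and SPSS fits these models. The sponsor should expect modest power, because the trial is not sized for attitude: an unadjusted comparison of 80% with 60% favourable at endline has about 53% power with 43 per arm. That is a reason to lead with the estimate and its interval, not a reason to keep the within-woman test.
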